1.2 Schematic

Figure 1 PROVENT Repeat Dose Sub-study Design

- Participants from PROVENT parent study who may benefit from a repeat dose of AZD7442.
- b Based on randomization in the parent study.
- Participants will be eligible for the sub-study once they have reached 12 ± 2 months post dose in the double-blind parent study. Therefore, in the AZD7442 group, the dosing interval between Dose 1 (parent study) and Dose 2 (SS-D1) will be approximately 12 months.
- For participants who have not undergone a Day 366 visit in the parent study, the Day 366 assessments will be performed at SS-D1.
- Participants in Group 3 are those who consented to receive extended AZD7442 doses and comprise those from USA sites Group 1 and Group 2 (approximately evenly distributed between groups) who already received Dose 2 and Dose 1 of AZD7442 on SS-D1, respectively. Participants in Group 3 will now receive additional AZD7442 doses approximately every 6 months and will be followed for approximately 6 months after receiving their last dose at SS-D366.

M, month; SS-D, sub-study day.

1.3 Schedule of Activities

Table 2, Table 3, and Table 4 summarize the schedule of activities for the PROVENT repeat dose sub-study for Group 1 (participants randomized to AZD7442 in the parent study),

Group 2 (participants randomized to placebo in the parent study), and Group 3 (participants from Group 1 or Group 2 who will receive additional AZD74442 repeat doses) respectively. On dosing days, all assessments are to be obtained pre-dose unless otherwise specified. For participants who have not undergone a Day 366 visit in the parent study, the Day 366 assessments listed in the tables should be performed at SS-D1. For participants who have already undergone the Day 366 visit in the parent study, only the SS-D1 assessments need to be performed.

Participants who present with or report a COVID-19 qualifying symptom(s) after SS-D1 will be instructed to initiate Illness Visits and will be tested locally for SARS-CoV-2 (Table 5). If negative at Illness Visit Day 1, the participant will be instructed to stop Illness Visits and continue with the sub-study scheduled assessments in Table 2, Table 3, or Table 4. If positive, the participant will be instructed to continue with all Illness Visits and will have additional assessments per Table 5.

Table 2 Schedule of Activities: Sub-Study Treatment and Follow-up Period for Group 1 (AZD7442 Participants from the PROVENT Parent Study)

Procedure	Parent study		Su	Early Discontinuation Visit	For details, see Section:					
Day ^a	Day 366 ^b	SS-D1 ^b	SS-D29	SS-D92	SS-D183	SS- D275	SS-D366	SS-D457		
Window (days)	± 61	NA	± 3	± 5	± 10	± 15	± 15	± 15]	
Informed consent (sub-study)		X (pre- dose)								A 3
Verify eligibility criteria		X (pre- dose)								5.1, 5.2
Targeted physical examination	X	X	X	X	X	X	X		X	8.2.1
Weight		X								8.2.1
Vital signs (including pulse oximetry)	X (pre-dose)	X (post- dose ^c)	X	X	X	X	X		X	8.2.2
Triplicate 12-lead ECG	X (pre-dose)		X		X		X		X	8.2.3
Serum chemistry	X (pre-dose)		X	X	X	X	X		X	8.2.4
Hematology	X (pre-dose)		X	X	X	X	X		X	8.2.4
Coagulation		X (pre- dose)	X	X	X	X	X		X	8.2.4
Urinalysis	X (pre-dose)		X	X	X	X	X		X	8.2.4
Cardiac biomarkers		X (pre- dose)	X		X		X		X	8.2.4
Troponin T/l		X (pre- dose)								8.2.4

Table 2 Schedule of Activities: Sub-Study Treatment and Follow-up Period for Group 1 (AZD7442 Participants from the PROVENT Parent Study)

Procedure	Parent study		Su		Early Discontinuation Visit	For details, see Section:				
Day ^a	Day 366 ^b	SS-D1 ^b	SS-D29	SS-D92	SS-D183	SS- D275	SS-D366	SS-D457		
Window (days)	± 61	NA	± 3	± 5	± 10	± 15	± 15	± 15		
Pregnancy test – urine (WOCBP only) ^d	X (pre-dose)	X (pre- dose)	х	X	X	Х	х		X	8.2.4.1
FSH (suspected postmenopausal women, < 50 years) ^e		X (pre- dose)								8.2.4.1
Concomitant medications	X		X	X	X	X	X		X	6.5
AZD7442 administration		Dose 2								6.1
Weekly telephone/email/text contacts - monitoring for COVID-19 qualifying symptoms and safety monitoring ^f	-			-						8.1.1, 8.3
Monthly telephone/email/text contacts - monitoring for COVID-19 qualifying symptoms and safety monitoring ^f					-			-		8.1.1, 8.3

Table 2 Schedule of Activities: Sub-Study Treatment and Follow-up Period for Group 1 (AZD7442 Participants from the PROVENT Parent Study)

Procedure	Parent study		Su	b-study Tr		Early Discontinuation Visit	For details, see Section:			
Day ^a	Day 366 ^b	SS-D1 ^b	SS-D29	SS-D92	SS-D183	SS- D275	SS-D366	SS-D457		
Window (days)	± 61	NA	± 3	± 5	± 10	± 15	± 15	± 15		
Documented SARS-CoV-2 RT-PCR test taken ≤ 3 days before SS-D1 ^g OR Rapid SARS-CoV-2 antigen test (for screening criteria)		X (pre- dose) ^h								8.6.1.1
NP swab for SARS-CoV-2 RT-PCR (central laboratory)		X (pre- dose) ⁱ								8.6.1.1
Serum sample for SARS- CoV-2 serology (anti- nucleocapsid) testing ^k	Х		X	Х	Х	X	X		X	8.5.2.2
Pharmacokinetics, pharma	codynamics, and	l ADA asse	ssments							
Serum sample for AZD7442 pharmacokinetic assessment	X		X	X	X	X	X		X	8.5.1
Serum sample for AZD7442 ADA assessment	X		X	X	X	X	X		X	8.5.2.1
Serum sample for SARS- CoV-2 nAbs assessment	X		X	X	X	X	X		X	8.5.3.1

Table 2 Schedule of Activities: Sub-Study Treatment and Follow-up Period for Group 1 (AZD7442 Participants from the PROVENT Parent Study)

Procedure	Parent study		Su	b-study Tro		Early Discontinuation Visit				
Day ^a	Day 366 ^b	SS-D1 ^b	SS-D29	SS-D92	SS-D183	SS- D275	SS-D366	SS-D457		
Window (days)	± 61	NA	± 3	± 5	± 10	± 15	± 15	± 15		
Nasal adsorption for exploratory assessments ^j	X				X		х		х	8.5.2.3
Safety assessments							•		•	
Check injection sites ^k		X (post- dose)								8.2.5
AEs ¹	-					\rightarrow	•	X ^m	X	8.3
SAEs, MAAEs, and AESIs ^{f,1}	-					→		X ^m	х	8.3
Other assessments										
Serum sample exploratory biomarkers	X		X	x	X	X	Х		х	8.5.2.5

To distinguish between sub-study visits and parent study visits the sub-study visits will be labeled as follows: the first sub-study visit Day 1 = SS-D1, sub-study visit Day 29 = SS-D29, and so on as applicable.

For participants who have not undergone a Day 366 visit in the parent study, the Day 366 assessments listed above should be performed at SS-D1. For participants who have already undergone the Day 366 visit in the parent study, only the SS-D1 assessments need to be performed. Day 366 assessments in the parent study will be used as baseline in the sub-study.

Perform 15 minutes (± 5 minutes) after both injections are complete.

If the urine pregnancy test is positive or indeterminate, a quantitative serum β-hCG will be performed by the central laboratory for confirmation. On SS-D1, a negative pregnancy test is required before the participant receives IMP.

- FSH will be analyzed at SS-D1 to confirm postmenopausal status only in women < 50 years of age who have been amenorrhoeic for ≥ 12 months. Until FSH is documented to be within menopausal range, the participant is to be considered of childbearing potential. For women aged ≥ 50 years, postmenopausal is defined as having a history of ≥ 12 months' amenorrhea prior to SS-D1, without an alternative cause, following cessation of exogenous sex-hormonal treatment.
- Weekly contact up to SS-D183 with participants to remind them to present to the study site for SARS-CoV-2 testing if they have qualifying symptoms. The Investigator will enquire about any COVID-19 symptoms from the past 7 days and other adverse events.

 Monthly contact with participants from SS-D183 to EOS, to assess overall safety. The Investigator will ask about any COVID-19 qualifying symptoms and cardiac events from the past month and other AEs. Participants should be reminded to present to the study site for SARS-CoV-2 testing if they have qualifying symptoms and to contact the site should they develop qualifying symptoms between each monthly contact.
- This test is not performed as part of the clinical study but must be available prior to enrollment.
- If a documented SARS-CoV-2 RT-PCR test is not available at screening, a rapid SARS-CoV-2 antigen test will be performed. Either test must be negative before dosing (see inclusion criteria in Section 5.1)
- Baseline sample, not a screening sample; results not needed prior to dosing.
- When test supplies are available, sampling should be performed.
- Perform immediately, 30 minutes (± 10 minutes) after both injections are complete, and prior to participant release (1 hour after IMP administration).

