- If a documented SARS-CoV-2 RT-PCR test is not available at screening, a rapid SARS-CoV-2 antigen test will be performed. Either test must be negative before dosing (see inclusion criteria in Section 5.1)
- i Baseline sample, not a screening sample; results not needed prior to dosing.
- When test supplies are available, sampling should be performed.
- ^k Perform immediately, 30 minutes (± 10 minutes) after both injections are complete, and prior to participant release (1 hour after IMP administration).
- After IMP administration, participants will be closely monitored for one hour before they can leave the site.
- ^m AEs, SAEs, MAARs, and AESIs will be assessed via a phone call at SS-D639.

For participants who have not undergone a Day 366 visit in the parent study, the Day 366 assessments listed above should be performed at SS-D1. For participants who have already undergone the Day 366 visit in the parent study, only the SS-D1 assessments need to be performed. Day 366 assessments in the parent study will be used as baseline in the sub-study.

The Day 366 Visit assessments in the parent study = baseline in the sub-study (ie, samples do not need to be collected twice). On dosing days, all assessments are to be conducted pre-dose unless otherwise specified.

ADA, antidrug antibody; AE, adverse event; AESI, adverse event of special interest; β-hCG, beta-human chorionic gonadotropin; COVID-19, coronavirus disease 2019; ECG, electrocardiogram; EOS, end of study; FSH, follicle-stimulating hormone; IMP, investigational medicinal product; MAAE, medically attended adverse event; NA, not applicable; nAb, neutralizing antibody; NP, nasopharyngeal; RT-PCR, reverse transcriptase polymerase chain reaction; SAE, serious adverse event; SARS-CoV-2, severe acute respiratory syndrome-coronavirus-2; SS-D, sub-study day; WOCBP, women of childbearing potential.

Table 4 Schedule of Activities: Extended Sub-Study Treatment and Follow-up Period for Group 3 (AZD7442 and Placebo Participants from the PROVENT Parent Study)

Procedure		Sub-stu	dy Treatn	nent and I	Follow-up Period			E/D Visit		For details, see Section
Month	6		7	9	12		13	18		
Day ^a	SS- D183	SS- D190	SS- D211	SS- D275	SS- D366	SS- D373	SS- D394	SS- D548		
Window	± 10		± 3	± 5	± 10		± 3	± 15		
Informed consent (reconsent)	X									A 3
Targeted physical examination	X (pre-dose)		X	X	X (pre-dose)		X	X	X	8.2.1
Vital signs (including pulse oximetry)	X a (pre- and post-dose)		X	X	X ^a (pre- and post-dose)		х	X	X	8.2.2

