8.2.2 Vital Signs

Vital signs, including heart rate, respiratory rate, pulse oximetry, blood pressure, and body temperature, will be performed as specified in the SoA (see Section 1.3). The participant should be resting prior to the collection of vital signs.

Situations in which vital sign results should be reported as AEs are described in Section 8.3.7.

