Appendix E Anaphylaxis

In adults, anaphylaxis is highly likely when any one of the following 3 criteria is fulfilled:

Acute onset of an illness (minutes to several hours) with involvement of the skin, mucosal tissue, or both (eg, generalized hives, pruritus or flushing, swollen lips, tongue and/or uvula)

AND AT LEAST ONE OF THE FOLLOWING:

- Respiratory compromise (eg, dyspnea, wheeze-bronchospasm, stridor, reduced peak expiratory flow, hypoxemia)
- Reduced BP (see number 3 below for definition) or associated symptoms of endorgan dysfunction (eg, hypotonia [collapse], syncope, incontinence)
- 2 Two or more of the following that occur rapidly after exposure to a likely allergen for that participant (minutes to several hours):
 - Involvement of the skin-mucosal tissue (eg, generalized hives, itch, flush, swollen lips, tongue and/or uvula)
 - Respiratory compromise (eg, dyspnea, wheeze-bronchospasm, stridor, reduced peak expiratory flow, hypoxemia)
 - Reduced BP (see number 3 below for definition) or associated symptoms (eg, hypotonia [collapse], syncope, incontinence)
 - Persistent gastrointestinal symptoms (eg, crampy abdominal pain, vomiting)
- Reduced BP after exposure to known allergen for that participant (minutes to several hours); for adults a systolic BP of less than 90 mmHg or greater than 30% decrease from that person's baseline BP (taken at or immediately prior to start of the IMP administration), whichever BP is lower.

The following definitions are provided for the purposes of this study:

Hypersensitivity reaction: An acute onset of an illness with involvement of the skin, mucosal tissue, or both after injection of IMP (but does not meet the definition of anaphylaxis described above).

To assist with the mitigation of these AEs, see Table 15, which categorizes reactions by severity of symptoms and proposes severity-specific treatment and offers guidance on management of IMP. Final treatment is at the discretion of the Investigator and should reflect local standard of care.

Table 15 An Approach to Management of Anaphylactic, Hypersensitivity, and Post-injection Reactions

Severity of symptoms	Treatment	Investigational product
Mild local reactions (During and post injection and hypersensitivity)	Evaluate participant, including close monitoring of vital signs.	Pause or hold additional IMP injection immediately.

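### Participants whose parent Day 366 visit came before SS-D1 have no pre-dose blood pressure scheduled for that dose, although Appendix E and Table 15 judge reactions against one

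*Protocol*

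**What the plan says.** Protocol Section 1.3 has one schedule per group. In Table 2 (Group 1) and Table 3 (Group 2), the vital-signs row is marked pre-dose under parent Day 366 and post-dose under SS-D1. The timing footnote for the SS-D1 cell reads "Perform 15 minutes (± 5 minutes) after both injections are complete".

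Participants without a Day 366 visit have the Day 366 assessments done at SS-D1, so they do get pre-dose vital signs. For the others the rule is: "For participants who have already undergone the Day 366 visit in the parent study, only the SS-D1 assessments need to be performed". Their earlier Day 366 values serve as the sub-study baseline.

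The general timing rule is "On dosing days, all assessments are to be obtained pre-dose unless otherwise specified".

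Appendix E defines reduced BP in adults as a "systolic BP of less than 90 mmHg or greater than 30% decrease from" the person's own "baseline BP (taken at or immediately prior to start of the IMP administration), whichever BP is lower". Table 15 of that appendix grades reactions partly by systolic change (≤20, >20 and ≥40 mmHg) from a value obtained before administration.

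The later dosing visits are handled differently. Table 3 at SS-D183 and Table 4 at SS-D183 and SS-D366 all schedule vital signs "pre- and post-dose".

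**The concern.** The schedule and the safety appendix do not match for one dose in one subset. Appendix E presupposes a BP taken when dosing starts or just before it. For a participant whose Day 366 visit was held earlier, nothing in the schedule asks for that reading at SS-D1.

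SS-D1 is the repeat dose for Group 1 and the first exposure to AZD7442 for Group 2. At stake is how a BP-based reaction to that dose is recognised and graded. Under Appendix E, skin or mucosal involvement with reduced BP is anaphylaxis; skin or mucosal involvement that falls short of the anaphylaxis definition is a hypersensitivity reaction. In Table 15 the severe category leads to permanent discontinuation of the product, while the moderate hypersensitivity category only says to stop. The grade given at SS-D1 could therefore bear on a later dose, such as Group 2's at SS-D183.

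**Working it through.** **Does any other text supply the reading?**

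- The pre-dose default in Section 1.3 yields where a cell says otherwise, and the SS-D1 vital-signs cell says post-dose.
- Section 8.2.2 refers back to the schedule and adds no reading of its own.
- The targeted physical examination at SS-D1 (Section 8.2.1) is not defined to include vital signs.
- Appendix E describes the reference BP but schedules none.
- The carried-forward Day 366 value is not a reading at dosing. Day 366 has a window of ±61 days, so it runs from 366 − 61 = Day 305 to 366 + 61 = Day 427. Entry at 12 ± 2 months covers about the same range. The gap could in principle reach 427 − 305 = 122 days. That is an upper bound, not an estimate.

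Table 2 repeats the pre-dose urine pregnancy test in both the Day 366 and SS-D1 columns. The authors could repeat an item where they wanted it on the day of dosing, and they did not do so for vital signs.

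**When does the reduced-BP limit depend on the missing value?** Let B be systolic BP at dosing. The two criteria coincide where 0.7 × B = 90, so B = 90 / 0.7 = 128.6 mmHg. The Appendix E wording joins the criteria with an *or* and then adds a clause about the lower BP. It can be read in two ways.

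- Reading 1, the lower limit governs: limit = min(90, 0.7 × B).
- Reading 2, either criterion suffices: limit = max(90, 0.7 × B).

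The documents give no BP distribution, so the baselines below are illustrative.

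| B (mmHg) | 0.7 × B | Reading 1 | Reading 2 |
|---|---|---|---|
| 100 | 70 | 70 | 90 |
| 110 | 77 | 77 | 90 |
| 120 | 84 | 84 | 90 |
| 128.6 | 90 | 90 | 90 |
| 140 | 98 | 90 | 98 |
| 150 | 105 | 90 | 105 |

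Under reading 1 the limit depends on B below about 129 mmHg. Under reading 2 it depends on B above about 129 mmHg. In the range where it depends on B, a reference that is 10 mmHg off moves the limit by 0.7 × 10 = 7 mmHg.

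- Reading 1 example: a post-dose 80 is reduced against a reference of 120 (limit 84) but not against 110 (limit 77).
- Reading 2 example: that same 80 is reduced whatever the baseline, because 80 < 90. A post-dose 100, however, is reduced against 150 (limit 105) but not against 140 (limit 98).

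So the gap exists under both readings, but the participants it touches differ.

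**How many participants?** The documents do not say. Section 9.2 gives 503 in the sub-study against about 500 planned. The amendment draws Group 3 from existing participants, and Group 3's doses already have vital signs before and after. Participants without an earlier Day 366 visit are unaffected.

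**The case against.** The strongest reply is that the schedule merely omits a line that Appendix E implies. Nothing forbids a same-day BP, and both the appendix and Table 15 tell sites which reading they use. This stands in part. A reader might infer that sites had to fall back on an earlier visit's BP. The documents do not support that; they show only that the schedule does not require the reading.

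A reader might also infer damage to the primary endpoint, since incidence of adverse events of special interest (AESIs) is one of its components. Section 8.3.4 lists anaphylaxis and other serious hypersensitivity reactions as a single AESI category, so moving a serious reaction between those labels changes nothing. Only a reaction that would be serious under one label and not under the other could alter AESI incidence, and it would remain an adverse event either way.

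Other safeguards limit the consequence:

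- Appendix E has routes to anaphylaxis that need no BP: respiratory compromise, symptoms of end-organ dysfunction and persistent gastrointestinal symptoms.
- Table 15 is guidance, and final treatment is left to the investigator.
- Participants are watched for one hour after dosing.
- Section 6.1.1 already withholds further product after an immediate hypersensitivity reaction between the injections.

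Finally, most SS-D1 visits may already have taken place. These replies limit the size of the point. None of them puts the reading into the schedule.

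**Conclusion.** The point holds as a minor inconsistency between the schedule and Appendix E. Participants whose Day 366 visit preceded SS-D1 have only post-dose vital signs scheduled at that dose. The reference for the >30% fall and for Table 15's systolic-change cues is therefore not provided by the plan. The table reading is firm.

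The size is uncertain. It depends on how many participants had an earlier Day 366 visit, how many sites took a BP anyway, and which reading of the Appendix E limit applies; the documents settle none of these. The limits and examples above show sensitivity and are not estimates of misclassification. The effect is confined to recognising and grading BP-based reactions at SS-D1, with at most a small effect on AESI incidence.

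**What to change.** In Tables 2 and 3, change the SS-D1 vital-signs cell to "pre- and post-dose" for anyone still to be dosed, whether or not Day 366 is complete. This matches SS-D183 in Table 3 and both dosing visits in Table 4. For participants already dosed without a same-day pre-dose BP, add a note that any BP-based reaction classification at SS-D1 lacked the Appendix E reference.

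The cost is one cell in each of two tables, a few minutes at a visit already being held, and one note.

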Cardiac biomarkers		X (pre- dose)	X		X (pre- dose)	X		X		X		X	8.2.4
Troponin T/l		X (pre- dose)											8.2.4
Pregnancy test – urine (WOCBP only) ^d		X (pre- dose)	X	Х	X (pre- dose)	X	Х	Х	X	Х		Х	8.2.4.1
FSH (suspected postmenopausal women, < 50 years) ^e		X (pre- dose)											8.2.4.1
Concomitant medications	х		X	Х	Х	X	X	Х		Х		Х	6.5
AZD7442 administration		Dose 1			Dose 2								6.1
Weekly telephone/email/text contacts - monitoring for COVID-19 qualifying symptoms and safety monitoring ^f	-			-									8.1.1, 8.3

Table 3 Schedule of Activities: Sub-Study Treatment and Follow-up Period for Group 2 (Placebo Participants from PROVENT Parent Study)

Procedure	Parent Study			Sı	ıb-study T	reatment	and Follo	w-up Per	iod			Early	For
Day ^a	Day 36 6 ^b	SS- D1 ^b	SS- D29	SS- D92	SS- D183	SS- D211	SS- D275	SS- D366	SS- D457	SS- D548	SS- D639	Discon- tinuation Visit	details, see Section
Window (days)	± 61	NA	± 3	± 5	± 10	± 3	± 5	± 15	± 15	± 15	± 15	Visit	50000
Monthly telephone/email/text contacts - monitoring for COVID-19 qualifying symptoms and safety monitoring ^f					L						-		
Documented SARS- CoV-2 RT-PCR test taken ≤ 3 days before SS-D1 ^g OR Rapid SARS-CoV-2 antigen test (for screening criteria)		X (pre- dose) ^h											8.6.1.1
NP swab for SARS- CoV-2 RT-PCR (central laboratory)		X (pre- dose) ⁱ											8.6.1.1
Serum sample for SARS-CoV-2 serology (anti-nucleocapsid) testing ^k	X (pre- dose)		Х	х	X (pre-dose)	х	х	х	х	х		х	8.5.2.2

Table 3 Schedule of Activities: Sub-Study Treatment and Follow-up Period for Group 2 (Placebo Participants from PROVENT Parent Study)

Procedure	Parent Study			Si	ub-study T	reatment	and Follo	w-up Per	iod			Early	For
Day ^a	Day 36 6 ^b	SS- D1 ^b	SS- D29	SS- D92	SS- D183	SS- D211	SS- D275	SS- D366	SS- D457	SS- D548	SS- D639	Discon- tinuation Visit	details, see Section
Window (days)	± 61	NA	± 3	± 5	± 10	± 3	± 5	± 15	± 15	± 15	± 15	VISIC	Section
Pharmacokinetics, pha	Pharmacokinetics, pharmacodynamics, and ADA assessments												
Serum sample for AZD7442 pharmacokinetic assessment	X (pre- dose)		х	Х	X (pre- dose)	Х	х	х	Х	х		X	8.5.1
Serum sample for AZD7442 ADA assessment	X (pre- dose)		Х	х	X (pre- dose)	Х	Х	Х	Х	Х		х	8.5.2.1
Serum sample for SARS-CoV-2 nAbs assessment	X (pre- dose)		Х	х	X (pre- dose)	Х	Х	Х	Х	Х		х	8.5.3.1
Nasal adsorption for exploratory assessments ^j	X (pre- dose)				X (pre- dose)			х		х		х	8.5.2.3
Safety assessments													
Check injection sites ^k		X (post- dose)			X (post- dose)								8.2.5
AEs ¹	•								→		X ^m	X	8.3
SAEs, MAAEs, and AESIs ¹	•								→		X ^m	X	8.3

Table 3 Schedule of Activities: Sub-Study Treatment and Follow-up Period for Group 2 (Placebo Participants from PROVENT Parent Study)

Procedure	Parent Study		Sub-study Treatment and Follow-up Period									Early	For
Day ^a	Day 36 6 ^b	SS- D1 ^b	SS- D29	SS- D92	SS- D183	SS- D211	SS- D275	SS- D366	SS- D457	SS- D548	SS- D639	Discon- tinuation Visit	details, see Section
Window (days)	± 61	NA	± 3	± 5	± 10	± 3	± 5	± 15	± 15	± 15	± 15	VISIC	Section
Other assessments													
Serum sample exploratory biomarkers	X (pre- dose)		X	X	X (pre- dose)	X	X	X	X	X		X	8.5.2.5

To distinguish between sub-study visits and parent study visits, the sub-study visits will be labeled as follows: the first sub-study visit Day 1 = SS-D1, sub-study visit Day 29 = SS-D29, and so on as applicable.

- ^c Perform 15 minutes (± 5 minutes) after both injections are complete.
- If the urine pregnancy test is positive or indeterminate, a quantitative serum β-hCG will be performed by the central laboratory for confirmation. At visits SS-D1 and SS-D183, a negative pregnancy test is required before the participant receives IMP.
- FSH will be analyzed at SS-D1 to confirm postmenopausal status only in women < 50 years of age who have been amenorrhoeic for ≥ 12 months. Until FSH is documented to be within menopausal range, the participant is to be considered of childbearing potential. For women aged ≥ 50 years, postmenopausal is defined as having a history of ≥ 12 months' amenorrhea prior to SS-D1, without an alternative cause, following cessation of exogenous sex-hormonal treatment.
- Weekly contact up to SS-D183 with participants to remind them to present to the study site for SARS-CoV-2 testing if they have qualifying symptoms. The Investigator will enquire about any COVID-19 symptoms from the past 7 days and other adverse events.

 Monthly contact with participants from SS-D183 to EOS, to assess overall safety. The Investigator will ask about any COVID-19 qualifying symptoms and cardiac events from the past month and other AEs. Participants should be reminded to present to the study site for SARS-CoV-2 testing if they have qualifying symptoms and to contact the site should they develop qualifying symptoms between each monthly contact.
- This test is not performed as part of the clinical study but must be available prior to enrollment.
- If a documented SARS-CoV-2 RT-PCR test is not available at screening, a rapid SARS-CoV-2 antigen test will be performed. Either test must be negative before dosing (see inclusion criteria in Section 5.1)
- i Baseline sample, not a screening sample; results not needed prior to dosing.
- When test supplies are available, sampling should be performed.
- ^k Perform immediately, 30 minutes (± 10 minutes) after both injections are complete, and prior to participant release (1 hour after IMP administration).
- After IMP administration, participants will be closely monitored for one hour before they can leave the site.
- ^m AEs, SAEs, MAARs, and AESIs will be assessed via a phone call at SS-D639.

For participants who have not undergone a Day 366 visit in the parent study, the Day 366 assessments listed above should be performed at SS-D1. For participants who have already undergone the Day 366 visit in the parent study, only the SS-D1 assessments need to be performed. Day 366 assessments in the parent study will be used as baseline in the sub-study.

The Day 366 Visit assessments in the parent study = baseline in the sub-study (ie, samples do not need to be collected twice). On dosing days, all assessments are to be conducted pre-dose unless otherwise specified.

ADA, antidrug antibody; AE, adverse event; AESI, adverse event of special interest; β-hCG, beta-human chorionic gonadotropin; COVID-19, coronavirus disease 2019; ECG, electrocardiogram; EOS, end of study; FSH, follicle-stimulating hormone; IMP, investigational medicinal product; MAAE, medically attended adverse event; NA, not applicable; nAb, neutralizing antibody; NP, nasopharyngeal; RT-PCR, reverse transcriptase polymerase chain reaction; SAE, serious adverse event; SARS-CoV-2, severe acute respiratory syndrome-coronavirus-2; SS-D, sub-study day; WOCBP, women of childbearing potential.

Table 4 Schedule of Activities: Extended Sub-Study Treatment and Follow-up Period for Group 3 (AZD7442 and Placebo Participants from the PROVENT Parent Study)

Procedure		Sub-stu	dy Treatn	nent and I	Follow-up Period			E/D Visit		For details, see Section
Month	6		7	9	12		13	18		
Day ^a	SS- D183	SS- D190	SS- D211	SS- D275	SS- D366	SS- D373	SS- D394	SS- D548		
Window	± 10		± 3	± 5	± 10		± 3	± 15		
Informed consent (reconsent)	X									A 3
Targeted physical examination	X (pre-dose)		X	X	X (pre-dose)		X	X	X	8.2.1
Vital signs (including pulse oximetry)	X a (pre- and post-dose)		X	X	X ^a (pre- and post-dose)		х	X	X	8.2.2
Triplicate 12-lead ECG	X (pre-dose)		X		X (pre-dose)		X	X	X	8.2.3
Serum chemistry	X (pre-dose)		X	X	X (pre-dose)		X	X	X	8.2.4
Hematology	X (pre-dose)		X	X	X (pre-dose)		X	X	X	8.2.4
Coagulation	X (pre-dose)		X	X	X (pre-dose)		X	X	X	8.2.4
Urinalysis	X (pre-dose)		X	X	X (pre-dose)		X	X	X	8.2.4
Cardiac biomarkers	X (pre-dose)		X		X (pre-dose)		X	X	X	8.2.4
Pregnancy test – urine (WOCBP only) ^b	X (pre-dose)		X	X	X (pre-dose)		X	X	X	8.2.4.1
Concomitant medications	X		X	X	X		X	X	X	6.5
AZD7442 administration	X				X					6.1
Virtual Safety Follow up one week post- AZD7442 administration ^c		Х				Х				
Monthly telephone/email/ text contacts - monitoring for COVID-19 qualifying symptoms and safety monitoring ^d	4							→		8.1.1, 8.3

Table 4 Schedule of Activities: Extended Sub-Study Treatment and Follow-up Period for Group 3 (AZD7442 and Placebo Participants from the PROVENT Parent Study)

Procedure		Sub-stud	dy Treatn	nent and I	ollow-up Period			E/D Visit		For details, see Section
Month	6		7	9	12		13	18		
Day ^a	SS- D183	SS- D190	SS- D211	SS- D275	SS- D366	SS- D373	SS- D394	SS- D548		
Window	± 10		± 3	± 5	± 10		± 3	± 15		
Serum sample for SARS-CoV-2 serology (anti-nucleocapsid) testing	X (pre-dose)		X	X	X (pre-dose)		X	X	X	8.5.2.2
Pharmacokinetics, pharmacodynamics, ar	ıd ADA assessme	nts		•		•				
Serum sample for AZD7442 pharmacokinetic assessment	X (pre-dose)		X	X	X (pre-dose)		X	X	x	8.5.1
Serum sample for AZD7442 ADA assessment	X (pre-dose)		X	X	X (pre-dose)		Х	Х	X	8.5.2.1
Serum sample for SARS-CoV-2 nAbs assessment	X (pre-dose)		X	X	X (pre-dose)		X	Х	х	8.5.3.1
Nasal adsorption for exploratory assessments ^e	X (pre-dose)				X (pre-dose)			X	X	8.5.2.3
Safety assessments	•			•		•				
Check injection sites ^f	X (post-dose)				X (post-dose)					8.2.5
AEs, SAEs, MAAEs, and AESIsg	-							—	X	8.3
Other assessments								_		
Serum sample exploratory biomarkers	X (pre-dose)		X	X	X (pre-dose)		X	X	X	8.5.2.5

Perform 15 minutes (± 5 minutes) after both injections are complete.

b If the urine pregnancy test is positive or indeterminate, a quantitative serum β-hCG will be performed by the central laboratory for confirmation. At visits SS-D183, SS-D366, and SS-D548, a negative pregnancy test is required before the participant receives IMP.

c AEs, SAEs, MAAEs, and AESIs, including injection site reactions, will be assessed via virtual phone call approximately one week after each dose.

- Monthly contact with participants to EOS to assess overall safety. The Investigator will ask about any COVID-19 qualifying symptoms and cardiac events from the past month and other AEs. Participants should be reminded to present to the study site for SARS-CoV-2 testing if they have qualifying symptoms and to contact the site should they develop qualifying symptoms between each monthly contact.
- When test supplies are available, sampling should be performed.
- f Perform immediately, 30 minutes (± 10 minutes) after both injections are complete, and prior to participant release (1 hour after IMP administration).
- After IMP administration, participants will be closely monitored for one hour before they can leave the site.

ADA, antidrug antibody; AE, adverse event; AESI, adverse event of special interest; β-hCG, beta-human chorionic gonadotropin; COVID-19, coronavirus disease 2019; E/D, early discontinuation visit; ECG, electrocardiogram; EOS, end of study; IMP, investigational medicinal product; MAAE, medically attended adverse event; nAb, neutralizing antibody; SS-D, sub-study day; SAE, serious adverse event; SARS-CoV-2, severe acute respiratory syndrome-coronavirus-2; WOCBP, women of childbearing potential.

Table 5 Schedule of Activities: Illness Visits (Participants with Qualifying Clinical Symptoms)

Procedure ^a	Site Visit	Н	Home Collection by Participant Site Visit for SARS-C Participants						For
Day ^b	IL-D1	IL-D3	IL-D5	IL-D8	IL-D11	IL-D14	IL-D21	IL-D28	details, see Section:
Window (days)	NA	± 1	± 1	± 2	± 2	± 2	± 2	± 2	Section.
Medical history	X					X	X	X	
Brief physical examination	X					X	X	X	8.2.1
Vital signs (including pulse oximetry)	X					X	X	X	8.2.2
Triplicate 12-lead ECG								X	8.2.3
Concomitant medication	←		•	•		•	—	•	6.5
Efficacy assessments	•								•
Saliva sample for viral shedding ^d	X	X	X	X	X	X	X	X	8.6.1.2
Nasopharyngeal swab			•	•		•			•
SARS-CoV-2 RT-PCR (local laboratory) ^e	X								8.6.1.1
SARS-CoV-2 RT-PCR (central laboratory), sequencing, respiratory panel	Х					X	X	X	8.6.1.1
Immunogenicity, Pharmacodyna	mics, and Pha	ırmacokinet	ics						
PBMCs for B-cell and T-cell responses ^e	X					X			8.5.2.4
Serum sample for AZD7442 pharmacokinetic assessment	X					X	X	X	8.5.1
Serum sample for SARS-CoV-2 nAbs assessment	X					X	X	X	8.5.3.1

Table 5 Schedule of Activities: Illness Visits (Participants with Qualifying Clinical Symptoms)

Procedure ^a	Site Visit	Home Collection by Participant Site Visit for SARS-CoV-2 Positive Participants Only ^c							For
Day ^b	IL-D1	IL-D3	IL-D5	IL-D8	IL-D11	IL-D14	IL-D21	IL-D28	details, see Section:
Window (days)	NA	± 1	± 1	± 2	± 2	± 2	± 2	± 2	Section.
Nasal adsorption for SARS- CoV-2 mucosal responses and exploratory assessments ^f	X					X		X	8.5.2.3
Serum sample for exploratory assessments	X					X	X	X	8.5.2.5
Safety assessments			•	•					•
SAEs, MAAEs, and AESIs	←						→		8.3
Telephone contact for safety monitoring		X		X					
Coagulation	X					X	X	X	8.2.4

Following availability of the SARS-CoV-2 RT-PCR results, only participants who test positive at ILD-1 will continue with the Illness Visits (ie, full visit series starting from IL-D1 and leading up to IL-D28), including any home collection requirements. Participants who test negative for SARS-CoV-2 at IL-D1 will be instructed to stop all Illness Visit assessments.

Note: The Illness Visit schedule is to be performed in addition to the scheduled visits in the main sub-study period (Table 2, Table 3, or Table 4). Where visits coincide, all assessments from the scheduled visit in Table 2, Table 3, or Table 4 and the Illness Visit should be performed.

AESI, adverse events of special interest; D, day; ECG, electrocardiogram; IL, illness visit; MAAE, medically attended adverse event; NA, not applicable; nAb, neutralizing antibody; PBMC, peripheral blood mononuclear cell; RT-PCR, reverse transcriptase polymerase chain reaction; SAE, serious adverse event; SARS-CoV-2, severe acute respiratory syndrome-coronavirus-2.

To distinguish between illness episodes the visits will be labeled as follows. For the first episode Illness Visit Day 1 = 1IL-D1, Illness Visit Day 3 = 1IL-D3 etc, and for the second episode 2IL-D1, 2IL-D3, and so on as applicable.

Where supported, home or mobile visits by study staff may substitute for site visits

To be collected when operationally viable.

A local test is required. If an immediate test result is not available, the participant should continue with the Illness Visit schedule until their result has been confirmed. Only if the local laboratory result is unavailable should the central laboratory result be used to assess continuation in Illness Visit schedule. In all instances both tests are required.

When test supplies are available, sampling should be performed.

